5.4 Duration of Study Participation

The study duration per subject will be approximately 23 weeks, with up to 4 weeks of screening, up to 7 weeks on treatment, and 3 months of follow-up.

5.5 Removal of Patients from Protocol

Patients will be removed from the study when any of the criteria listed in [Section 6.6](#) apply. If any of these criteria are met the PI will be notified and the reason for study removal and the date the patient was removed will be recorded. The patient should be followed-up per protocol.

5.6 Subject Replacement

Subjects who withdraw from the study prior to their PREHAB session 1 will be replaced.

Subjects who attend at least the first session will be evaluable for both the primary and secondary endpoint analysis. To be evaluable for exploratory endpoints subjects will need to complete the 3 month follow up visit.

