PAR-Q	Physical Activity Readiness Questionnaire
PI	Principal Investigator
PREHAB	Prehabilitation
PROMIS-29	Patient-Reported Outcomes Measurement Information System
PROMIS Cancer Function	Patient-Reported Outcomes Measurement Information System Cancer Function
QMC	Quality Management Core
SOC	Standard of Care
SOCCI	Samuel Oschin Comprehensive Cancer Institute
UPIRSO	Unanticipated Problems Involving Risk to Subjects or Others

STUDY SCHEMA

Primary endpoint: Feasibility of a PREHAB program evaluated by attendance. The program will be considered feasible if at least 50% of participants attend at least 60% of exercise sessions.

PREHAB- Prehabilitation

STUDY SUMMARY

Title	A Supervised Prehabilitation Exercise Program for Patients with Pancreatic Cancer
Short Title	Exercise program for pancreatic cancer
Protocol Number	IIT2021-18-[name]-PREHAB
Phase	Pilot
Methodology	Single Arm
Study Duration	12 Months
Study Center(s)	Single Center
Objectives	The primary objective is to test the feasibility of a supervised prehabilitation program for patients with pancreatic cancer.
Number of Subjects	16 subjects
Diagnosis and Main Inclusion Criteria	
Main Inclusion Criteria:
 
 -Pancreatic cancer diagnosis (any stage) -Age ≥ 18 years -Independent ambulation and activities of daily living -Godin-Shephard Leisure-Time Physical Activity Questionnaire score of ≤ 23 -Physically able to participate in study assessments -Answers no to all questions on PAR-Q OR is cleared to participate by the study physician -Written informed consent obtained from subject and ability for subjects to comply with the requirements of the study
Study Product(s), Dose, Route, Regimen	Supervised exercise PREHAB program
Duration of administration	6 weeks
Reference therapy	None
Statistical Methodology	The primary analysis will test the hypothesis of feasibility using an one-sided exact Binomial test at 25% significance level. If 10 or more patients attend a minimum of 60% of exercise sessions during the initial 6-week period, then the study will be declared feasible.

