8.0 STATISTICAL CONSIDERATIONS

8.1 Sample Size and Randomization

We plan to enroll 16 patients to reach 80% power testing the hypothesis that the proportion of patients with attendance at least 60% of exercise sessions during the initial 6-week period is greater than 50% using an one-sided exact Binomial test at 25% significance level. The actual significance level is 22.7%.

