9.3 Registration Procedures/Enrollment Procedures

All patients will be tracked following written informed consent. Those patients who are consented to participate in the clinical trial but do not meet one or more criteria required for participation during the screening phase will be listed as screen failures on the master list of consented subjects. Eligible subjects, as determined by screening procedures and verified by a treating investigator, will be registered on study at Cedars Sinai Medical Center by the Study Coordinator.

Issues that would cause treatment delays after registration should be discussed with the PI. If a patient does not receive protocol therapy following registration, the patient's registration on the study may be canceled. The Study Coordinator should be notified of cancellations as soon as possible.

Assignment of Subject ID: The study teams will track all subjects who sign consent using OnCore. Subjects found to be ineligible will be recorded as screen failures. Subjects found to be eligible will be registered using a three-digit numeric ID that follows the standard Samuel Oschin Comprehensive Cancer Institute (SOCCI) format (001, 002, etc.).

A) Eligibility Verification

Prior to registration, all subjects must undergo an eligibility verification by the study-specific research staff. Minimal risk studies are exempt from SOCCI Quality Management Core (QMC) central eligibility checklist review and eligibility verification. QMC central eligibility checklist review and eligibility verification for all subjects enrolled is performed only if requested by the PI at any time during the life of the study.

For patients requiring a protocol exception request and/or waiver due to eligibility concerns, refer to Section 9.7.2, Protocol Exceptions and Eligibility Waivers for instructions.

B) Registration

After eligibility is verified, each site will assign the subject a study number and site staff will then register the patient in OnCore®.

Registration is completed as follows:

- Assignment of a patient study number

- Enter the patient in OnCore
- Notify the treating physician that a subject has gone on study and the anticipated start date

Oversight by the PI is required throughout the entire registration process.

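### If anyone registered withdraws before session 1, the primary attendance proportion describes starters only and can overstate feasibility for participants; an all-registered companion figure should be prespecified

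*Combined protocol and SAP*

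**What the plan says.** Section 5.6 has two relevant rules. The first is replacement: "Subjects who withdraw from the study prior to their PREHAB session 1 will be replaced". The second is evaluability: "Subjects who attend at least the first session will be evaluable for both the primary and secondary endpoint analysis". Read together, they make the 16 in the primary denominator (Section 2.4.1) people who came at least once.

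Section 9.3 adds a discretionary step. "If a patient does not receive protocol therapy following registration", the registration may be cancelled.

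The claim itself is not limited to starters. The study schema says: "The program will be considered feasible if at least 50% of participants attend at least 60% of exercise sessions". Section 8.1 speaks of enrolling: "We plan to enroll 16 patients to reach 80% power". The test is set up "using an one-sided exact Binomial test at 25% significance level", against a null proportion of 50%, and Sections 2.4.1 and 8.3 put the cut-off at 10.

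Section 8.2 gives a different analysis set: only eligible subjects who took part in at least 60% of sessions. No section plans a result for all registered subjects, or a starting rate, beside the primary result.

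**The concern.** In many efficacy trials, replacing people who never start is a minor matter. Here the endpoint is whether patients come. Someone who consents, is found eligible, is registered and then attends no session has 0% attendance, and the plan drops that observation and fills the place with someone else. The denominator is selected on the first instance of the outcome, so relative to all registered subjects any shift can only be upward.

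There is room for this to happen. Up to 14 days may separate Baseline from the first session (Section 6.2), patients with any stage of disease are eligible (Section 4.1), and concurrent neoadjuvant therapy is expected (Section 6.2.4). At stake is what the trial may conclude: that patients offered the program will attend it, or only that those who begin it keep coming. The plan has no output that would let a reader tell the two apart.

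**Working it through.** **Inputs.** n = 16, null proportion 0.50, one-sided exact binomial test at 25% (Section 8.1); cut-off of 10 (Sections 2.4.1 and 8.3). The non-start rate r is not in the documents, so it is assumed and varied.

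**Step 1: reproduce the plan's figure.** P(X ≥ 10 | n = 16, p = 0.5) = 0.2272. Section 8.1 says "The actual significance level is 22.7" percent, which agrees. Ten is the smallest cut-off at n = 16 with a level of at most 25%. The alternative behind the 80% power is not stated; the rule has 80.0% power at a true proportion of 0.690 and 82.5% at 0.70.

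**Step 2: add non-starters to the boundary result.** Count each non-starter as not reaching 60% and recompute P(X ≥ 10 | n, 0.5):

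| Non-starters | Result | One-sided p | Exact test at 25% |
|---|---|---|---|
| 0 | 10/16 = 62.5% | 0.2272 | passes |
| 1 | 10/17 = 58.8% | 0.3145 | fails |
| 2 | 10/18 = 55.6% | 0.4073 | fails |
| 3 | 10/19 = 52.6% | 0.5000 | fails |
| 4 | 10/20 = 50.0% | 0.5881 | fails |
| 5 | 10/21 = 47.6% | 0.6682 | fails |

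The last row is the first to fall below the schema's 50%.

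**Step 3: how far the reversal extends.** The largest number of non-starters at which p stays at or below 0.25 is:

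- 10 of 16 starters: none
- 11 of 16: two (11/18, p = 0.2403)
- 12 of 16: three (12/19, p = 0.1796)
- 13 of 16: five (13/21, p = 0.1917)

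Exactly 10 of 16 has probability 8008/65536 = 0.122 at a true rate of 0.50. That is 0.122/0.227, or about 54%, of passing results. At a true rate of 0.70 (assumed) it is about 20% of them.

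**Step 4: chance of declaring feasibility.** Suppose the proportion who both start and reach 60%, among all registered, is 0.50. Among starters the rate is then 0.50/(1 − r), and the chance of passing is P(X ≥ 10 | 16, 0.50/(1 − r)):

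| Assumed r | Rate among starters | Chance of passing |
|---|---|---|
| 0% | 0.500 | 22.7% |
| 5% | 0.526 | 29.6% |
| 10% | 0.556 | 38.3% |
| 15% | 0.588 | 48.8% |
| 20% | 0.625 | 60.9% |

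**The case against.** The strongest reply is that this is a choice of estimand. Section 5.6 states the rule openly and in advance. For the population it defines, the error rate is the stated 22.7%. In the 20% scenario the true rate among starters is 62.5%, so declaring feasibility for starters would not be an error. The objective in Section 2.1 sets no uptake target. This stands: a reader might infer from 38.3% or 60.9% that the type I error of the planned test is wrong, and the documents do not support that. Those figures measure the starters' test against a claim about everyone registered. They matter because the schema words its claim for participants.

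Second, a reader might infer that the primary result will overstate feasibility, or that one non-starter would overturn it. Neither follows. The shift is zero if everyone starts. The one-subject reversal holds only at exactly 10/16, and only for the exact test re-derived at n = 17, where the cut-off moves to 11 and discreteness lowers the attained level to 16.6%. Under the schema's 50% wording 10/17 still passes, and the bare count of 10 in Section 8.3 is still met.

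Third, not every non-start reflects on the program. A physician's decision, pregnancy (Section 6.6) or laboratory values below threshold (Section 6.2.4) may be the cause. That is a reason to report causes, not to omit the count.

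Fourth, the text is narrower than it may seem. Section 5.6 replaces those who withdraw; someone who never starts for another reason is not expressly replaced, though still not evaluable. Cancellation under Section 9.3 is discretionary, and the summary of changes says language in that section was updated to match standard protocol text. It is weak evidence of a deliberate denominator rule.

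Finally, much of the information is already collected. Section 9.3 tracks everyone who consents, and Section 5.5 records the date of and reason for removal. What is missing is a planned display.

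**Conclusion.** The point holds conditionally. If any registered eligible subject does not start, the primary proportion applies to starters and can overstate feasibility for the participants named in the schema. The size depends on a non-start rate that the documents do not give. With a true all-registered rate of 50% and assumed non-start rates of 5% to 20%, the chance of declaring feasibility is 29.6% to 60.9%, against 22.7% with none. These figures count every non-starter as not reaching 60%.

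The test on 16 starters remains valid for starters. What the plan does not support, once anyone has been excluded, is an unqualified conclusion about participants. This is an inexpensive improvement that changes what the trial can conclude; it is not a flaw that invalidates the design.

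**What to change.** Keep the replacement rule and the test on 16 starters. Then:

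- **Sections 5.6 and 8.3:** prespecify a companion proportion reaching 60% among all registered eligible subjects. Count every subject who never starts, whether withdrawn or otherwise not evaluable, as not reaching it. Report it with an exact 95% interval beside the primary result, with the number of and reasons for non-start.
- **Conclusion:** word it as feasible among patients who start whenever anyone was excluded.
- **Section 9.3:** state that cancelled registrations stay in this count.
- **Section 8.2:** reconcile it with Section 5.6. Read literally, restricting the analysed data to those with at least 60% participation makes the primary rate 100% by construction, so the denominator stays contradictory if only the other sections are amended.

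The cost is a few sentences and no new data collection, since consented subjects and reasons for removal are already recorded. The downside is that the companion figure may be less favourable than the primary one.

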2.4.3 Exploratory Endpoints

2.4.3.1 Impact on sarcopenia we will be measured using changes in hand grip strength and the short physical performance battery measured at Baseline, Post-Intervention Evaluation and 3-month Follow Up. Changes in Muscle Mass measured at Baseline and 3-month Follow Up will also be utilized.

2.4.3.2 Health-related quality of life will be measured by changes in the PROMIS-29 and PROMIS Cancer Function 3D Profile¹⁶ scores measured at Baseline, Post-Intervention Evaluation and 3-month Follow Up.

2.4.3.3 Functional Performance will be measured by changes in the 6-minute walk test and physical performance metrics scores measured at Baseline, Post-Intervention Evaluation and 3-month Follow Up.

2.4.3.4 Hospitalizations and length of stay will be recorded from medical record review and a telephone follow-up with the patient and their caregivers at the 3-month follow up. Only hospitalizations post Baseline will be recorded.

2.4.3.5 Post-operative outcomes will be recorded from medical record review and a telephone follow-up with the patient and their caregivers at the 3-month follow up. Only operations post Baseline will be recorded. Post-operative complications will be assessed by the investigator retrospectively using the Clavien-Dindo classification system^{17,18}.

2.4.3.6 Physical Activity and Sleep will be measured by continuous activity and sleep monitoring by the Fitbit wrist worn device. The Fitbit will be worn from Baseline through to the 3-month Follow Up.

2.4.3.7 Impact of the online Pain guide will be measured by the Patient Global Impression questionnaire administered at the Post Intervention Evaluation Visit.

2.4.3.8 Impact on weight and BMI will be measured using changes in weight and BMI measured at Baseline, Post-Intervention Evaluation and 3-month Follow Up.

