6.4.3 SOC Abdomen CT scan

- Document date of closest SOC Abdomen CT scan (ok if occurs outside of the 3 month \pm 14 days window)

6.4.4 Healthcare Utilization Assessment (May be assessed by chart review, in-person discussion at visit and/or phone call)

- Number of hospitalizations
- Reason for hospitalization
- Days hospitalized
- Disposition: continued therapy, hospice, death, other
- If underwent resection then evaluate post-op complications - Post-operative complications will be assessed using the Clavien-Dindo classification system^{17,18}

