8.2 Data Sets Analyzed

Data from all eligible subjects who have participated in a minimum of 60% of the exercise sessions will be analyzed.

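### Section 5.6 limits every exploratory endpoint to subjects who complete the 3-month visit, which discards observed post-intervention data and conflicts with how utilization outcomes are collected

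*Combined protocol and SAP*

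**What the plan says.** Section 5.6 (Subject Replacement) holds two evaluability rules. For the main endpoints: "Subjects who attend at least the first session will be evaluable for both the primary and secondary endpoint analysis". For the rest: "To be evaluable for exploratory endpoints subjects will need to complete the 3 month follow up visit". No other section relaxes the second rule.

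Section 8 does not define an exploratory analysis set and does not say how deaths or missed visits are handled. Section 8.3 promises descriptive summaries, but names only the secondary endpoints. Section 8.2 brings in a different restriction: "Data from all eligible subjects who have participated in a minimum of 60% of the exercise sessions will be analyzed".

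The exploratory endpoints (2.4.3) draw on several sources:

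- **Utilization (2.4.3.4):** "Hospitalizations and length of stay will be recorded from medical record review and a telephone follow-up with the patient and their caregivers".
- **Post-operative outcomes (2.4.3.5):** "Post-operative outcomes will be recorded from medical record review and a telephone follow-up with the patient and their caregivers".
- **How utilization is assessed (6.4.4):** "May be assessed by chart review, in-person discussion at visit and/or phone call". The fields collected include "Disposition: continued therapy, hospice, death, other".
- **Physical measures and PROMIS (2.4.3.1 to 2.4.3.3):** taken at baseline, at the Post-Intervention Evaluation (6.3.2, within 14 days of the last session) and at 3 months.
- **Pain portal (2.4.3.7):** "Patient Global Impression questionnaire administered at the Post Intervention Evaluation Visit", with no later measurement.

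**The concern.** Whether a subject counts depends on something that happens after the intervention: being alive, well enough and willing to complete a visit at the end of a 3-month follow-up period (5.4). That has two consequences.

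First, data already in hand are thrown away. A subject may finish the program, complete every post-intervention test and then miss the later visit. Under 5.6 that subject contributes nothing, even to an endpoint such as Patient Global Impression that is never measured at 3 months.

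Second, the subjects removed are unlikely to be a random subset. Enrollment is open to any disease stage (4.1.1), and most participants are expected to be on neoadjuvant therapy at the same time (6.2.4). Those in hospital, in hospice or recovering from complications are the likeliest to miss the visit, and theirs are the events that 2.4.3.4 and 2.4.3.5 are meant to count. A single-arm study of 16 has no comparator that might share the same selection.

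**Working it through.** **1. The rule set against the data sources.**

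| Exploratory data | Is completing the 3-month visit needed to have the data? | Effect of 5.6 as written |
|---|---|---|
| Walk test, grip, performance battery, PROMIS at the Post-Intervention Evaluation | No; already observed | Discarded if the visit is missed |
| Patient Global Impression | No; collected only post-intervention | Discarded if the visit is missed |
| Hospitalizations, length of stay, post-operative complications | No; records and phone contact, including caregivers | Not evaluable on the plain wording |
| Disposition of death | Cannot coexist with an attended visit | Category could not occur among evaluable subjects if completing means attending |
| Muscle mass on CT | Needs a later scan, but 6.4.3 accepts one outside the visit window | Discarded if the visit is missed |

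**2. The plan's own figure.** The plan gives no figure for the exploratory endpoints. Its one checkable figure belongs to the primary rule: P(X ≥ 10 | n = 16, p = 0.5) = 14893/65536 = 0.2272, matching the stated 22.7%. The 3-month visit plays no part in that calculation.

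**3. Hospitalization: how far completers can differ from all subjects.** The documents give no dropout or admission rates, so the inputs are assumed. Let d of 16 subjects not complete, let 20% of completers be hospitalized, and let the non-completers' rate be r. The rule reports 20% in every case. The all-patient figure is [(16 − d) × 20% + d × r] / 16.

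| d | r = 20% | r = 60% | r = 80% | r = 100% |
|---|---|---|---|---|
| 2 | 20% | 25% | 27.5% | 30% |
| 4 | 20% | 30% | 35% | 40% |
| 6 | 20% | 35% | 42.5% | 50% |

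Example for d = 4, r = 100%: (12 × 20% + 4 × 100%)/16 = 6.4/16 = 40%. If non-completers had no admissions at all, the d = 4 figure would be (12 × 20%)/16 = 15%, so the sign depends on r.

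**4. Six-week walk change.** Assume completers gain 30 m and that all d non-completers have a 6-week value. The all-patient mean is [(16 − d) × 30 + d × c] / 16, where c is the non-completers' mean change.

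| d | c = +30 m | c = 0 | c = −30 m |
|---|---|---|---|
| 2 | 30 m | 26.25 m | 22.5 m |
| 4 | 30 m | 22.5 m | 15 m |
| 6 | 30 m | 18.75 m | 7.5 m |

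**5. Precision.** With a common standard deviation, the standard error scales as 1/√n. If k of the 4 non-completers have a 6-week value, the rule inflates it by √((12 + k)/12). At k = 4 this is √(16/12) = 1.155; at k = 2 it is √(14/12) = 1.080; at k = 0 it is 1. About 15% is therefore the ceiling for this scenario.

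**6. Interaction with 8.2.** Three sessions a week for 6 weeks make 18, and 60% of 18 is 10.8, so 8.2 requires 11 sessions. A subject who stopped after 8 sessions but attended the Post-Intervention Evaluation would stay excluded under 8.2 even if 5.6 were corrected.

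**The case against.** **Utilization may not be lost.** Section 6.4.4 allows the 3-month assessment by chart or phone and lists death as an outcome. A reader could fairly hold that this part of the follow-up can be completed without attending. That stands in part: for utilization and post-operative outcomes the documents are inconsistent, and a definite loss of data is not established. The looser reading sits badly with the plain wording of 5.6, and it does nothing for the 6-week tests and questionnaires.

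**Progression does not exclude anyone.** A reader might infer that progressing patients are dropped. The documents do not support this. Progression is not among the removal reasons in 6.6, and 5.5 says removed patients should still be followed. Only a missed visit excludes.

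**The direction is not shown.** A reader might also infer that the rule demonstrably biases results towards benefit. The documents contain no dropout, death or admission rates. Early death shortens time at risk, so a non-completer may have fewer admissions, and step 3 shows that the sign can reverse. For utilization the study estimates no within-study benefit, because only events after baseline are recorded and there is no control arm; the likely harm is an understated count.

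**The endpoints are exploratory.** This stands, and it limits the consequence.

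**Conclusion.** The point holds for all exploratory endpoints, with different force. For the Post-Intervention Evaluation measures, 5.6 as written discards valid observed data and nothing elsewhere restores them. For hospitalization and post-operative outcomes, 5.6 conflicts with 2.4.3.4, 2.4.3.5 and 6.4.4, and the passages must be reconciled.

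The likely effect is that hospitalization and complications are understated and functional change overstated. This rests on the assumption that subjects who miss the visit fare worse than those who attend; if the two groups are alike, the bias is zero. The size cannot be derived from the documents. With 4 non-completers of 16 and 20% of completers hospitalized, the completer figure of 20% stands against an all-patient figure of 20% to 40% for non-completer rates of 20% to 100%.

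It would be wrong to conclude that the feasibility result is compromised by this sentence. The primary and secondary endpoints have their own evaluability rule in 5.6, attendance at the first session.

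**What to change.** Replace the exploratory sentence in 5.6 with evaluability defined by endpoint, and align 8.2 with it so that the 60% attendance restriction does not exclude the same patients.

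- **Utilization, disposition and post-operative outcomes:** all subjects attending at least one session. Ascertain by record review and, where possible, the planned phone contact with patient and caregivers, up to death, withdrawal of consent or 3 months. Report follow-up time. Record review alone would use less than 2.4.3.4 and 2.4.3.5 plan and could miss admissions elsewhere.
- **Change endpoints:** all subjects with a baseline and the relevant post-baseline value, summarized at each visit from available data. Report deaths and missing visits with reasons. A mixed model is optional in a descriptive study of this size.
- **Patient Global Impression:** all portal users who completed it at the Post-Intervention Evaluation.
- **Completer-only results** may be kept as a sensitivity summary.

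Cost: because 5.6 is protocol text, this needs a short amendment with IRB approval before implementation (9.7.4), plus chart or phone follow-up for a few non-completers, which 6.4.4 already permits. No visits or procedures are added.
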